During clinical trials, elevations 3 times the upper limit of normal (ULN) or greater in liver transaminases occurred in 8% of patients treated with fingolimod 0.5 mg compared to 2% of placebo patients. Elevations of 5 times the upper limit of normal occurred in 2% of patients on fingolimod and 1% of patients on placebo. Serum transaminase levels returned to normal within approximately 2 months after discontinuation of fingolimod.

If repeat ALT/AST values reach 5 times the ULN, the study drug will be interrupted until the results return within the normal range. More frequent monitoring should be instituted, including serum bilirubin, alkaline phosphatase (ALP) and other evaluations per discretion of the investigator. The study drug may be re-started once results return within normal range and per discretion of the investigator.

Patients who develop symptoms suggestive of hepatic dysfunction, such as unexplained vomiting, abdominal pain, fatigue, anorexia, jaundice or dark urine, should have liver enzymes checked, and fingolimod should be discontinued if significant liver injury is confirmed. Re-initiation of study drug will be dependent on whether or not another cause of liver injury is determined, and on the benefits to the patient of resuming therapy versus the risks of recurrence of liver dysfunction and per the discretion of the investigator.

More frequent liver monitoring may be instituted based on the clinical judgement in the below condition:

- For participants with normal ALT and AST and TBIL value at baseline: detection of elevated ALT/AST values of $>3.0 \times$ ULN and total bilirubin $> 2.0 \times$ ULN
- For participants with elevated AST or ALT or TBIL value at baseline: detection of elevated [AST or ALT $> 2 \times$ baseline] OR [AST or ALT $> 300\text{U/L}$] (whichever occurs first) combined with [TBIL $> 2 \times$ baseline AND $> 2.0 \times$ ULN]

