Patients should be monitored for signs and symptoms of any hepatic injury. Measure liver transaminase and bilirubin levels promptly in patients who report symptoms that may indicate liver injury, including new or worsening fatigue, anorexia, right upper abdominal discomfort, dark urine, or jaundice. In this clinical context, if the patient is found to have ALT/AST values of $>3.0 \times$ ULN with total bilirubin $> 2.0 \times$ ULN, treatment with fingolimod may be interrupted based on the clinical judgement. Treatment should not be resumed if a plausible alternative etiology for the signs and symptoms cannot be established, because these patients are at risk for severe drug-induced liver injury.

Because fingolimod exposure is doubled in patients with severe hepatic impairment, these patients should be closely monitored, as the risk of adverse reactions is greater.

Re-initiation of the study drug shall be considered once the liver enzymes are within the normal reference range and/or patients have clinically recovered from liver injury signs based on your clinical judgement, and kindly reach out to Medical Advisor at Novartis for any further clarification. In case it is agreed to re-start the study drug, weekly liver function test may be performed for patient's safety. Advise patients that they should contact their physician if they have any unexplained nausea, vomiting, abdominal pain, fatigue, anorexia, or jaundice and/or dark urine. The deterioration of new elevations above 2 times the ULN with worsening of liver injury clinical signs/symptoms based on investigator's clinical judgement may lead to permanent discontinuation of study drug in the best interest of patient's safety.

An interruption or discontinuation of the study drug should be clearly documented and reflected on Dosage Administration Record eCRF. AE/SAEs need to be filed as appropriate.

Guidance on monitoring of participants with notable lymphopenia

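### Protocol Appendix 7 gives two incompatible restart conditions after a confirmed ALT/AST rise to 5 x ULN: normal enzymes, or normal enzymes and/or clinical recovery

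*Protocol*

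**What the plan says.** All the relevant text is in Protocol Section 16.7 (Appendix 7), under the guidance on elevated liver function tests. It contains four statements about restart.

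- **Rule A, repeat ALT/AST at 5 x ULN.** "If repeat ALT/AST values reach 5 times the ULN, the study drug will be interrupted until the results return within the normal range". It continues: "The study drug may be re-started once results return within normal range and per discretion of the investigator".
- **Rule B, symptoms with confirmed significant liver injury.** The drug is discontinued. "Re-initiation of study drug will be dependent on whether or not another cause of liver injury is determined", and also on benefit against the risk of recurrence and on the investigator's discretion.
- **Rule C, symptoms with ALT/AST above 3 x ULN and total bilirubin above 2 x ULN.** Treatment may be interrupted on clinical judgement. "Treatment should not be resumed if a plausible alternative etiology for the signs and symptoms cannot be established".
- **Rule D, the general restart paragraph, with no trigger named.** Restart is to be considered once enzymes are "within the normal reference range and/or patients have clinically recovered from liver injury signs based on your clinical judgement". Sites may contact the sponsor's Medical Advisor for clarification. The next sentence covers the case where a restart has been agreed.

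Protocol 10.2.1 sends sites to Section 16.7 for the definitions of liver events and triggers and leaves further actions to the investigator. It does not rank the restart statements.

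**The concern.** Rule A has one laboratory gate: enzymes must be normal before restart. Rule D joins the same gate to clinical recovery with *and/or*, and under the *or* reading either is enough. Rule D does not exclude participants held under Rule A, so sites can apply different restart conditions to the same participant and each can cite the protocol.

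This is first a safety matter, because it concerns re-exposure after a marked liver enzyme elevation. Appendix 7 and Protocol 1.1 both put the return to normal at roughly 2 months after stopping, so the two readings could differ by weeks off drug.

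There are smaller consequences for the data:

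- The length of the interruption decides whether first-dose monitoring is repeated. After the first month of treatment the threshold is more than 14 days (Protocol 6.7.2 and 8.4.4.1).
- Exposure and compliance subtract every day without drug (SAP 2.4.1).
- TEAEs causing interruption and TEAEs leading to permanent discontinuation are summarised separately (SAP 2.8.1).

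**Working it through.** The plan states no figure for this point. The check is a comparison of the rules, plus one line of arithmetic on reach.

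**Step 1. The rules side by side.**

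| Rule | Trigger | Restart condition |
|---|---|---|
| A | Repeat ALT/AST at 5 x ULN | Results normal, and investigator discretion |
| B | Symptoms and confirmed significant liver injury | Another cause is one factor, with benefit-risk and discretion |
| C | Symptoms, ALT/AST > 3 x ULN and bilirubin > 2 x ULN | No resumption without a plausible alternative cause |
| D | None stated | Enzymes normal and/or clinically recovered, on clinical judgement; restart is then considered |

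**Step 2. A against D.** Take a participant whose repeat ALT reached 5 x ULN, who had signs of liver injury that have resolved, and whose ALT is still above normal.

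- Under A, the hold continues and restart is not available.
- Under D, read with *or*, clinical recovery is enough for restart to be considered.

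A does not permit restart at that time, and D opens it. If D means *and*, the conflict disappears for this participant. The text allows both readings.

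**Step 3. C against D.** Take a symptomatic participant with the combined elevation, no alternative cause found, and enzymes later normal. D says restart is to be considered; C says treatment should not resume. Both can be obeyed: the question is raised under D and answered under C. This is a gap in precedence, not a contradiction.

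**Step 4. B against C and D.** B treats another cause as one factor among several, whereas C makes its absence a bar in a narrower group. B and C point the same way and can be read as general and specific. D does not say that it yields to either.

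**Step 5. Overlap of triggers.** One participant can be symptomatic with ALT at 5 x ULN or more and bilirubin above 2 x ULN, and so fall under all four statements. Separate triggers alone therefore do not settle which statement governs.

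**Step 6. Reach.** Inputs: about 100 participants (Protocol 3 and 5); transaminases at or above 5 x ULN in 1.8% on 0.5 mg (Protocol 1.1; Appendix 7 rounds this to 2%).

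Expected number = 100 x 0.018 = 1.8, or about 2.

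This is a loose upper figure for Rule A, for two reasons. The 1.8% is not stated to be confirmed on repeat, which Rule A requires. It is also reported for asymptomatic elevations, whereas the participant in Step 2 had signs to recover from. The documents give no rate for symptomatic elevations or for the combined bilirubin case, so no number can be put on Rules B and C.

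**The case against.** The strongest reply is that Rule D only sets when restart may be discussed. It asks for clinical judgement, refers sites to the sponsor's Medical Advisor, and goes on to the case where restart is agreed. On that view a reader who infers that the protocol permits restart on clinical recovery alone goes too far. That is correct: D permits consideration and does not order or by itself authorise restart. It does not remove the conflict with A, because A leaves nothing to consider until results are normal. The Medical Advisor would be working from the same two paragraphs.

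A reader might also infer a three-way contradiction in which D overrides the bar in Rule C. The documents do not support this. C is a specific prohibition for a defined group, with its reason given, and a general paragraph in the same section does not cancel it. Step 3 shows that both can be followed. What stands is that the order of precedence is nowhere stated.

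A reader might further take the 8.0% with transaminases at or above 3 x ULN (Protocol 1.1) to mean about 8 affected participants per 100. That fails too: 3 x ULN alone triggers none of Rules A, B or C.

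Two further points against the concern carry weight. A participant who never had signs of liver injury fits the clinical-recovery branch poorly, so the clear overlap of A and D is mainly in symptomatic participants. The analysis consequence is also small: the primary analysis uses data up to the end of the treatment period whether on or off drug (SAP 2.5.3), so at most a very few participants would move in descriptive safety and exposure tables.

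**Conclusion.** The point holds as one contradiction and one lesser gap, and the appendix is wrong as written. The contradiction is between the hold after repeat ALT/AST at 5 x ULN and the general restart paragraph: for a clinically recovered participant with enzymes still raised, they give opposite answers and nothing ranks them. The gap is the unstated order between the general paragraph and the two rules on an alternative cause.

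The expected reach of the 5 x ULN rule is at most about 2 per 100, assuming that the historical 1.8% carries over to this population and that every such elevation is confirmed on repeat. The reach of the symptomatic and combined cases is unknown from the documents. The importance lies in participant safety and consistent conduct across sites, not in the primary estimate. The conclusion depends on the *or* reading of *and/or* being open, which the wording allows. It takes no view on which restart condition is clinically right.

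**What to change.** Reconcile the restart statements in Appendix 7. For each trigger (repeat ALT/AST at 5 x ULN; symptomatic confirmed injury; symptomatic combined transaminase and bilirubin elevation), state which restart condition applies. In the general paragraph, say whether *and* or *or* is meant and to which triggers it applies. State which statement takes precedence when a participant meets more than one trigger. The sponsor's clinical team must decide the rule.

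The cost is revised appendix wording and a letter to sites. No analysis in the SAP needs to change.

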MS	Multiple Sclerosis
NB	Negative binomial
[REDACTED]	[REDACTED]
NMPA	National Medical Products Administration
PDS	Programming Datasets Specifications
PK	Pharmacokinetics
PRO	Patient-reported Outcomes
PT	Preferred Term
RMS	Relapsing MS
SAE	Serious Adverse Event
SAF	Safety Set
SAP	Statistical Analysis Plan
SBP	Systolic Blood Pressure
SCR	All screened subjects
SOC	System Organ Class
TEAE	Treatment Emergent AE
TFLs	Tables, Figures, Listings

ULN	Upper Limit of Normal
VAS	Visual Analog Scale
WBC	White blood cell
WHO	World Health Organization

1 Introduction

The purpose of this Statistical Analysis Plan (SAP) is to describe the implementation of the statistical analysis planned in the protocol for study CFTY720D2419.

There will be one report resulting from this SAP: The clinical study report (CSR) of the D2419 study.

The final CSR will be completed after the final database lock.

This document is consistent with the current study protocols (version 03 original protocol).

1.1 Study design

This is a 24-month, open-label, multicenter, interventional, single-arm study to collect efficacy, safety and health outcome data of fingolimod (Gilenya) 0.5 mg/day in approximately 100 relapsing multiple sclerosis (RMS) subjects in China.

The study will consist of three Phases (see [Figure 1-1](#)):

Screening (up to 1 month): After signing informed consent, subjects will enter a Screening Phase to determine eligibility according to inclusion and exclusion criteria.

[figure not shown]
The investigator must ensure that all subjects meet the inclusion and exclusion criteria to be eligible to enter the study.

Treatment Period (24 months): On visit Day 1, all eligibility criteria will be confirmed, including a pre-dose ECG and vital signs. The first dose of study drug will be taken in the clinic on Day 1 and the subject will be monitored for at least 6 hours after the first dose administration before discharge. Refer to [\[Protocol Section 16.5\]](#) for Guidance for monitoring of subjects taking their first dose of the study drug.

Then the subjects should come to site and be evaluated at month 1 and then every three months till the end of treatment up to 24 months.

Follow Up (2 months): Subjects who completed Treatment Period will return for the Follow-up visit 2 months after the last dose of study drug.

Figure 1-1 Study design

1.2 Study objectives and endpoints

Table 1-1 Objectives and related endpoints

Objective(s)	Endpoint(s)
Primary objective(s)	Endpoint(s) for primary objective(s)

To evaluate the efficacy of fingolimod 0.5mg on annualized relapse rate (ARR) in subjects with RMS treated for up to 24 months.	
Annualized relapse rate (ARR)
Secondary objective(s)	Endpoint(s) for secondary objective(s)

To evaluate the safety and tolerability of fingolimod 0.5 mg in subjects with RMS treated for up to 24 months.	
Adverse events (AE) and serious adverse events (SAE)Laboratory tests (hematology, biochemistry)Vital signsElectrocardiogram (ECG)Ophthalmology

To evaluate the efficacy of fingolimod 0.5 mg on MRI lesions.	
T1 hypo-intense lesion number and volume; T2 lesion volume, new/newly enlarged T2 lesion number; Gd-enhancing T1 lesion number and volume.

2 Statistical methods

2.1 Data analysis general information

Novartis statistical and programming team will be performing the CSR analysis as planned in this document unless otherwise specified. The Statistical Analysis System (SAS) 9.4 and/or R 3.6.1 or higher versions will be used.

Unless otherwise stated, summary tables/figures/listings will be on all subjects in the respective analysis sets. Categorical data will be presented as frequencies and percentages. For continuous data, mean, standard deviations, median, 25th and 75th percentiles (optional), minimum and maximum will be presented.

For efficacy analyses in the final CSR, all available data until EOT (i.e. excluding the data collected in the safety follow-up part) will be considered and no other cut-offs will be applied.

For safety analyses in the final CSR, only data up to and including the safety cutoff of 45 days (5 times the half-life of fingolimod, 9 days) after the last dose administration of study drug will be considered. For safety analyses on the follow-up period, all data (including assessments or events more than 45 days after the last dose of study drug) will be considered.

Presentation of p-values: p-values from statistical tests will be presented with 3 decimal places, or as <.001 where applicable. Statistically significant p-values will be flagged with an asterisk. In general, this is when p-values ≤ 0.05 .

2.1.1 General definitions

The table below summarizes some general definitions to be used in the rest of the document.

Table 2-1 General Definitions

Study treatment/Study drug	The investigational drug (fingolimod) will be referred as study treatment or study drug.
Study Day 1 or Day 1	The date of first administration of study drug/first dose date.
Study Day	All other study days will be labeled relative to Day 1. For events with dates on or after Day 1, study day for the event is calculated as (event start date – first dose date + 1). For events with dates before Day 1, study day for the event is calculated as (event start date – first dose date). Day 0 will not be used.
Duration of an event	Duration of an event is calculated as (event end date – event start date +1).
1 month	30 days; to be used in determining target days of scheduled visits
Day post-study drug discontinuation	Day post-study drug discontinuation for a particular event is calculated as (event start date – study drug discontinuation date).

Baseline	Baseline is the last assessment with non-missing value obtained prior to the first administration of study drug. No visit windows will be needed for the identification of baseline assessment. For pulse and blood pressure vital sign values, the baseline is the average of the non-missing values of the 3 measurements taken on the last visit prior to the first administration of study drug.
On-treatment period	On-treatment period includes days from the first dose date until the last dose date. This definition applies to efficacy analyses only. For calculation of compliance to study drug administration, same definition will be used.
Off-treatment period	Off-treatment period includes days after the last dose date. This definition applies to both efficacy and safety analyses.
Safety cutoff	Safety cutoff: Unless explicitly otherwise stated (e.g. SAEs and deaths), data up to and including the safety cutoff of 45 days after permanent study drug discontinuation will be included in the analysis and data beyond this time point for a given subject will be excluded from the safety analysis. The safety cutoff of 45 days (5x9 days) takes the half-life of the investigational drug into consideration. The safety cutoff applies to safety analyses only.
Nominal visits	Nominal visits are defined as all scheduled visits as per the clinical study protocol including the EOS and EOT visits. The definition of nominal visit excludes unscheduled visits.
End of Study (EOS)	EOS, used in the context of individual subjects, refers to EOS visit.
End of Treatment (EOT)	EOT refers to EOT visit. Only subjects who prematurely discontinue study drug but agree to continue to follow the schedule of assessments in the treatment period will have EOT visit.
End of treatment period date	This date is the date of discontinuation/study phase completion as recorded in the Treatment disposition CRF page.
Last assessment on drug	It is the last assessment with non-missing value taken before or on the date of last administration of study drug. No visit windows will be needed for the identification of the last assessment on drug evaluation.

2.1.2 Visit windows

2.1.2.1 Visit windows for treatment period

Visit-windows will be used for both efficacy and safety data summaries by visit. Visit windows define a time period “around” the targeted visit date as defined in the evaluation schedule of the clinical study protocol. Visit-windows are non-overlapping and defined without gaps between

consecutive visit windows. The width of visit windows may vary over the course of the study period.

Baseline assessments are defined in [Section 2.1.1](#) and do not require a visit window.

The purpose of visit windows is to analyze data based on the actual study days (rather than "nominal" visits). E.g. if a subject's Month 1 visit is delayed; it is possible that the Month 1 data be re-aligned to visit-window Month 2 and be summarized under Month 2.

- For **efficacy analyses** all nominal visits (i.e. excluding unscheduled visits) will be mapped into one of the defined visit-windows.

-For **safety analyses** all visits (scheduled and unscheduled) will be mapped to visit windows. Safety data from unscheduled visits may be reported separately if applicable.

It is possible that more than one assessment of a subject fall into a particular visit-window. [Section 2.1.2.3](#) deals with the statistical approaches to handle multiple visits in a given visit-window.

Tables displaying summary statistics "by visit" will also use the term *visit-window* as column header; this is to remind the reviewer that multiple assessments of a subject might be summarized. Below tables provide visit-windows definitions for applicable parameters.

Table 2-3 Visit-windows for MRI

Visit-window	Start day	Target Day	End day
Month 12	1	360	540
Month 24	541	720	900

Table 2-4 Visit-windows for routine laboratory values

Visit-window	Start day	Target Day	End day
Month 1	1	30	60
Month 3	61	90	135
Month 6	136	180	225
Month 9	226	270	315
Month 12	316	360	450
Month 18	451	540	630
Month 24	631	720	810

Table 2-5 Visit-windows for vital signs*

Visit-window	Start day	Target Day	End day
Month 1	1	30	60
Month 3	61	90	135
Month 6	136	180	225
Month 9	226	270	315
Month 12	316	360	405
Month 15	406	450	495
Month 18	496	540	585
Month 21	586	630	675
Month 24	676	720	765

*Data collected from Day 1 protocol scheduled visit will not be mapped to the visit windows due to different data collection on those visits.

Table 2-6 Visit-windows for Electrocardiogram (ECG)

Visit-window	Start day	Target Day	End day
Month 1	1	30	60
Month 3	61	90	135
Month 6	136	180	270
Month 12	271	360	450
Month 18	451	540	630
Month 24	631	720	810

*Data collected from Day 1 protocol scheduled visit will not be mapped to the visit windows due to different data collection on those visits.

For vital signs, the mean of the FTY Day 1 pre-dose value will be used as FTY baseline. If unavailable, the last available (including unscheduled) value before the first dose will be used. Missing Day 2 pre-dose values are not imputed. Day 2 assessments are only collected in subjects that meet Day 1 protocol monitoring guidelines.

For ECG, the FTY Day 1 pre-dose value will be used as FTY baseline. If unavailable, the last available (including unscheduled) value before the first dose will be used. Missing Day 2 pre-dose values are not imputed. Day 2 assessments are only collected in subjects that meet Day 1 protocol monitoring guidelines.

